	Visit 1 Week -3 to 0	Visit 2 Week 0	Visit 3 Week 4	Visit 4 Week 8	Visit 5 Week 12	Visit 6 Week 16	Visit 7 Week 20	Visit 8 Week 24	Visit 9 Week 28	Visit 10 Week 32	Visit 11 Week 36	Termination visit Week 40 / Drop-out Visit	Unscheduled Visit
Informed consent	X												
Eligibility criteria	X												
Demographic and baseline characteristics	Х												
Med. hist./Prior medication	X												
Standard ECG	X												
Pregnancy test	X											X	
Blood for viral markers	X											Х	
Blood sample for D-dimers	X												
Randomization		X ²											
Physical examination ²	X		Х			Х			Х			Х	Х
Vital signs³	X	Х	Х	Х	Х	Х	Х	Х	Х	Х	Х		Х
Body weight ²	X					Х			Х				
Safety laboratory ²	X	X	Х	X	Х	Х	Х	Х	Х	Х	X	Х	Х
Serum IgG ²	X	Х	Х	Х	Х	Х	Х	Х	Х	Х	Х	Х	Х
Enzymes ²	X	X	Х	Х	Х	Х			Х			Х	Х
Biomarkers blood sample	X					Х						Х	
Blood sample for additional safety lab ⁵		Х				Х			Х			Х	
Direct Coombs' test⁵		X				X			X			X	
CSM for TIS determination ²	X	X	Х	Х	Х	Х			Х			X	X
CDASI ²		Х	Х	Х	Х	Х			Х			Х	X
SF-36 Health Survey ²		X	_			Х						Х	
Wells score for DVT ⁴	Х	Х	Х	Х	Х	Х	Х	Х	Х	Х	X		Х
Wells score for PE⁴	Х	X	Х	Х	Х	Х	Х	Х	Х	Х	X		Х
Infusion of IMP ¹		X*	X*	X*	X*	X**	X**	X**	X*	X*	Χ#		
Adverse event monitoring		Throughout the study											
Concomitant medication			Throughout the study										

¹ Infusion cycles can last between 2 to 5 days, consisting of 2 or more infusion episodes.

²Before IMP administration;

³ Before, during and after each infusion episode;

⁴ At screening and after each infusion cycle;

⁵ Before and after infusion cycle;

^{*}Blinded infusion of either placebo or 2.0 g/kg Octagam 10%

^{**}Unblinded infusions of 2.0 g/kg Octagam 10%;

[figure not shown]
[#]In case subject is stable on the 2.0 g/kg Octagam 10% dose, they can be switched to 1.0 g/kg Octagam 10%, at the discretion of the investigator

[name]

[name]

PROTOCOL SIGNATURES

This study is intended to be conducted in compliance with the protocol, Good Clinical Practice and applicable regulatory requirements.

Clinical Project Manager Signature Date

Octapharma Pharmazeutika Produktionsges.m.b.H.

[name]

Manager Biometrics

Signature

Date

18 June 2019

Date

Octapharma Pharmazeutika Produktionsges.m.b.H.

Version 12 18-Jun-2019

PROTOCOL SIGNATURES

This study is intended to be conducted in compliance with the protocol, Good Clinical Practice and applicable regulatory requirements.

Signature

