6.1.5 Visit 6 (Week 16; End of First Period, Start of Extension Period)²

The following assessments will be performed:

Before infusion cycle:

- SF-36v2.
- Physical examination.
- Vital signs and body weight.
- Blood sample for safety laboratory (hematology and clinical chemistry).
- Blood sample for additional safety lab parameters "Panel 1" (serum haptoglobin and plasma-free hemoglobin).
- Direct Coombs' test (if positive, the antibodies responsible for the positive Coombs' test will be eluted to investigate their specificity (anti-A, anti-B or anti-D)).
- Blood sample for serum IgG.
- Blood samples for enzymes.
- Blood sample for biomarkers of disease activity.
- CSM.
- CDASI.

Before, during and after each infusion episode:

- Administration/Infusion of IMP (2.0 g/kg [20 mL/kg] Octagam 10% given in infusion episodes over 2 to 5 consecutive days).
- Vital signs before, at least once during and at least 1 hour after each infusion episode.

At least 1 hour after the infusion cycle:

- Blood sample for additional safety lab parameters "Panel 2" (serum haptoglobin, hemoglobin, plasma-free hemoglobin, LDH).
- Direct Coombs' test (if positive, the antibodies responsible for the positive Coombs' test will be eluted to investigate their specificity (anti-A, anti-B or anti-D)).
- Wells probability score for DVT. If score is likely for DVT (≥2 points), perform Doppler scan and take blood sample for D-dimers.
- Wells probability score for PE.

In addition, AEs will be monitored and concomitant medications will be documented.

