6.1.10 End-of-Study (Final Examination) Visit 12 (Week 40; Extension Period) or Drop-out Visit

The final examination is performed 4 weeks after the last IMP administration.

The following investigations will be performed:

- SF-36v2.
- Physical examination.
- Blood sample for safety laboratory (hematology and clinical chemistry).
- Blood sample for additional safety lab parameters "Panel 1" (serum haptoglobin and plasma-free hemoglobin)
- Direct Coombs' test (if positive, the antibodies responsible for the positive Coombs' test will be eluted to investigate their specificity (anti-A, anti-B or anti-D)).
- Blood sample for serum IgG.
- Blood samples for enzymes.

- Blood sample for viral markers.
- Blood sample for biomarkers of disease activity.
- CSM.
- CDASI.
- Monitoring of AEs.
- Documentation of concomitant medication.
- Pregnancy test.

After the Final Examination, the clinical study is considered completed for the subject. No further study-related assessments will be performed, unless safety concerns (e.g., ongoing AEs) require follow-up.

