6.1.11 Time Windows Used in this Study, Including Tolerances

In this study, the following time windows and tolerances apply:

 Table 4:
 Time Windows Used in this Study

Time Point	Time stated	Tolerance
Interval between visits / infusion cycles	4 weeks	± 4 days
Interval between infusion episodes	1 day (next day)	15 – 30 hours
Vital signs	before IMP administration of infusion episode	≤ 60 minutes
	after each IMP administration	≥ 60 minutes
Direct Coombs' test	before first IMP administration of infusion cycle	≤ 4 hours
	after last IMP administration of infusion cycle	≥ 60 minutes
Wells probability score for DVT	after IMP administration of last infusion episode of a cycle	≥ 60 minutes
Wells probability score for PE	after IMP administration of last infusion episode of a cycle	≥ 60 minutes

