6.2.3 Premature Termination of the Study

Both the Investigator and the Sponsor reserve the right to terminate the study at any time. In this event, any necessary procedures will be arranged on an individual study basis after review and consultation by both parties. In terminating the study, the Sponsor and the Investigator will ensure that adequate consideration is given to the protection of the subjects' interests.

Regulatory authorities and IECs/IRBs should be informed in accordance with national regulations.

Early termination of the study as a whole or by centre may apply for the following reasons:

6.2.3.1 Early Termination of the Entire Clinical Study

At any time, the study as a whole will be terminated prematurely if:

- New toxicological or pharmacological findings or safety reports invalidate the earlier positive benefit-risk-assessment.
- If more than 3 TEEs (i.e. ischemic stroke, transient ischemic attack, cerebral infarction, cerebrovascular accident, cerebral thrombosis, embolic infarctions, [acute] myocardial infarction, deep vein thrombosis, pulmonary embolism, venous thrombosis excluding thrombophlebitis or infusion site thrombosis) are observed during the first (controlled) period of the study, fulfilling the following criterion:
 - associated with Octagam 10% treatment;

AND

if less than half of the number of TEEs reported as associated with Octagam 10% are observed during the first (controlled) period of the study, fulfilling the following criterion:

associated with placebo treatment.

- .
- For TEEs observed on or after the cut-off date of 04-Jul-2018 (since introduction of reduced maximum infusion rate of 0.04 mL/kg/min) TEE rates (per 100 patientmonths) will be calculated as follows:
 - Ro = 100* Number of TEEs observed on or after the cut-off date in patients last treated with Octagam / Total person-months of patients on Octagam since the cut-off date
 - Rp = 100* Number of TEEs in patients last treated with Placebo / Total person-months of patients on Placebo. Rp is based on the whole study period, no cut-off is applied)

These rates will be calculated on basis of the actual last treatment.

The study as a whole will be terminated

• if Ro exceeds Rp by more than 1.0

AND

 at least 4 TEEs have been observed in the Octagam group after the cut-off date of 04-Jul-2018.

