7.3.5 Adverse Events of Special Interest (AESI)

The following AEs are defined as AESI:

- thromboembolic events (TEEs);
- hemolytic transfusion reactions (HTRs).

For these AESI, the general definitions and procedures that are described elsewhere in Section 7.3 apply as well. TEEs must be reported as SAE as described in Section 7.3.3. Premature termination criteria related to AESI are defined in Section 6.2.3.1.

7.3.5.1 Thromboembolic Events (TEEs)

There is clinical evidence of an association between IGIV administration and TEEs such as ischemic stroke, transient ischemic attack, cerebral infarction, cerebrovascular accident, cerebral thrombosis, embolic infarctions, [acute] myocardial infarction, deep vein thrombosis (DVT), pulmonary embolism (PE), venous thrombosis.

TEEs will be monitored as follows:

• Wells criteria for assessment of probability for possible DVTs at each visit ([25] modified according to NICE Clinical Guideline 144, 2012):

Pre	Present	
	☐ Active cancer (treatment ongoing, within 6 months, or palliative)	
	☐ Paralysis, paresis or recent plaster immobilization of the lower extremities	
	☐ Recently bedridden for 3 days or more or major surgery within 12 weeks requiring general or regional anesthesia	
	Localized tenderness along the distribution of the deep venous system	+1
	Entire leg swollen	+1
	Calf swelling at least 3 cm larger than asymptomatic side	+1
	☐ Pitting edema confined to the symptomatic leg	
	Collateral superficial veins (non-varicose)	+1
	Previously documented DVT*	+1
	An alternative diagnosis is at least as likely as DVT	-2
Cli	nical Probability Simplified Score DVT likely ≥2 points DVT unlikely ≤1 point	

^{*}Note: This is also an exclusion criterion

• If the Well's DVT probability score is ≥2, then a Doppler screening for DVT will have to be completed (recommended: Doppler using color duplex sonography) and a blood sample will have to be taken for D-dimers.

 Wells criteria for assessment of probability for possible PE at each visit ([26]; modified according to NICE Clinical Guideline 144, 2012):

Present		Score
	 Clinical signs and symptoms of DVT (minimum of leg swelling and pain with palpation of the deep veins) 	
	An alternative diagnosis is less likely than PE	3
	Heart rate > 100 beats per minute	1.5
	Immobilization for more than 3 days or surgery in the previous 4 weeks	1.5
	Previous DVT/PE	1.5
	Hemoptysis	1
	☐ Malignancy (on treatment, treated in the last 6 months, or palliative)	

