11.1. Adverse Events

All reported AEs will be coded according to MedDRA.

An AE is defined as treatment-emergent, if first onset or worsening is during the treatment period. Only treatment-emergent AEs (TEAEs) are accounted for in the analysis.

For each TEAE, the time relative to the start of the infusion cycle will be calculated and the TEAE will be classified as infusional AE if the onset is during the infusion cycle or within 72 hours after the end of the last infusion episode of the respective infusion cycle/visit.

All reported events will be listed and tabulated in full detail; in particular the following key figures will be presented:

- Total number of TEAEs reported by severity and overall
- Number of related TEAEs by severity and overall
- Number of TEEs and HTRs
- Number of adverse drug reactions (ADRs) and suspected ADRs
- Number of infusional AEs by severity and overall
- Number of infusion cycles with infusional AEs

Narratives will be prepared describing each death, other SAEs, and other significant AEs that are judged to be of special interest because of clinical importance, including all TEEs and HTRs reported.

The number and percentage of patients with TEAEs and the number of TEAEs will be summarized by actual treatment, unless otherwise specified, i.e. any adverse event will be considered to be associated with the most recent treatment administered, Octagam or Placebo, when summarizing the data.

Patients who are switched to the other treatment during the first study period will therefore be considered to be at risk for adverse events in both treatment groups. AE tables for the first period will summarize data within the following four groups:

1. Octagam – before or no switch
2. Octagam – after switch from Placebo
3. Placebo – before or no switch
4. Placebo – after switch from Octagam

Moreover, exposure adjusted incidence rates of TEEs will be presented under Octagam and Placebo treatment. These rates will be calculated per 100 patient months on corresponding treatment, and will be presented together with 95% confidence intervals, based on Poisson distribution. Rates will be shown under Octagam and Placebo treatment in the first period and under Octagam treatment over the total study period and for the extension period only. Also all rates will be calculated including only infusions before reduction of the infusion rate, those after reduction of the infusion rate, and including all infusions.

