11.5.2. Wells Scores

To identify all occurrences of DVT and PE, Wells' probability scores will be assessed at all visits. If the DVT score is likely for DVT (≥ 2 points), a Doppler scan is performed, and D-dimers are evaluated. These parameters will be combined into a dedicated listing to facilitate the assessment of these TEAEs of special interest.

12. Reporting Conventions

The following reporting conventions will be adopted for the presentation of study data. These conventions will enhance the review process and help to standardize presentation with common notations.

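### After Screening, scheduled Wells DVT/PE scores come only after an infusion cycle and are absent at Week 40/Drop-out, contrary to Protocol 7.3.5.1 and SAP 11.5.2, and the Ro/Rp stopping rule does not say that a TEE is attributed by onset date

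*Protocol*

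**What the plan says.** **Schedule.** Footnote 4 of the flowchart (Protocol Table 1) times the Wells scores "At screening and after each infusion cycle". Table 4 (Section 6.1.11) repeats this as at least 60 minutes "after IMP administration of last infusion episode of a cycle". The visit lists in Sections 6.1.2 to 6.1.8 agree. At Week 16 (6.1.5) both scores stand under "At least 1 hour after the infusion cycle", and that cycle is open-label Octagam. A score of 2 or more for DVT triggers a Doppler scan and D-dimers.

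**Last visit.** Section 6.1.10 says "The final examination is performed 4 weeks after the last IMP administration". Its list contains no Wells score, and both Wells rows of Table 1 are blank in the Week 40/Drop-out column.

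**Intent.** Section 7.3.5.1 provides for "Wells criteria for assessment of probability for possible DVTs at each visit", with matching wording for PE. SAP 11.5.2 says "To identify all occurrences of DVT and PE, Wells' probability scores will be assessed at all visits".

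**Attribution.** SAP 11.1 states that "any adverse event will be considered to be associated with the most recent treatment administered, Octagam or Placebo, when summarizing the data". Protocol 9.2.1 and SAP 7 tie this to the treatment being given when the event occurs. For the study-level stopping rule, Protocol 6.2.3.1 counts in Ro the TEEs observed from the cut-off date onward in patients last treated with Octagam, and adds: "These rates will be calculated on basis of the actual last treatment".

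**The concern.** TEEs are a named safety emphasis, and their rates can end the whole study. Two features of the schedule bear on how completely and under which treatment they are counted.

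First, the interval after the last cycle has no closing score. This affects completers, whose last interval is on Octagam. It also affects drop-outs and subjects who leave at Week 16 without an infusion, including those switched from Octagam to placebo. The time counts in the denominator, while ascertainment in the numerator is weaker.

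Second, where treatment changes, the scheduled score comes after the new treatment has been given. This holds at Week 16 for continuing placebo subjects. It also holds in both directions at a First Period switch (Weeks 8 and 12). An event that belongs to the earlier treatment may first be picked up when the subject is already last treated with the other one.

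The effects do not all point the same way. An event moved from placebo to Octagam makes Octagam look worse. A missing closing score on Octagam makes it look better.

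**Working it through.** The plan gives no figure of its own on this point. Its planned total of 94 supplies 47 per arm at 1:1.

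**1. The passages side by side**
- After the cycle only: Table 1 footnote 4, Table 4, Sections 6.1.2 to 6.1.8.
- No score at the last visit: Table 1, Section 6.1.10.
- At every visit: Section 7.3.5.1, SAP 11.5.2.
- Scores without an infusion: Screening (6.1.1) and unscheduled visits (6.1.9). So the score does not depend on an infusion.

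The first two groups cannot both be followed together with the third.

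**2. Length of the unscored interval**
- Inputs: 28 days between cycle starts, tolerance ±4 days (Table 4); cycles of 2 to 5 days, so the last episode falls on day +1 to +4.
- Nominal: 28 − 4 = 24 to 28 − 1 = 27 days.
- With the tolerance: 24 − 4 = 20 to 32 − 1 = 31 days.
- Share of the 112 placebo days before Week 16: 24/112 = 21% to 27/112 = 24%.
- Share of Octagam time at the end of the study: 24/280 to 27/280 = 9% to 10% for subjects randomized to Octagam; 24/168 to 27/168 = 14% to 16% for those coming from placebo.
- In full 4-week blocks: Octagam person-weeks = 47 × 40 + 47 × 24 = 3,008; last blocks = 94 × 4 = 376; 376/3,008 = 12.5%.

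**3. Effect on Ro − Rp if one TEE moves from placebo to Octagam**
- Placebo person-months with full follow-up: 47 × 112/30.44 = 173.
- Octagam person-months since the cut-off are not in the documents. Assumed range: 200 to 600. The maximum, if all Octagam exposure fell after the cut-off, is 47 × (280 + 168)/30.44 = 692.
- Rp falls by 100/173 = 0.58. Ro rises by 100/600 = 0.17 to 100/200 = 0.50.
- Total shift: 0.74 to 1.08 (from unrounded terms). The rule's margin is 1.0.
- Wider assumptions (placebo time 70% to 100% of 173, Octagam time 25% to 100% of 692) give 0.72 to 1.40.
- Illustration at 350 Octagam months: 3 Octagam and 1 placebo event give 300/350 − 100/173 = 0.28, with fewer than 4 Octagam events, so no stop. Recorded as 4 and 0, they give 400/350 = 1.14 with 4 events, so both conditions are met.

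**4. The first-period TEE rule**

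This rule needs more than 3 Octagam events and fewer than half that number on placebo. With 4 and 2 it is not met, because 2 is not less than 2. If one placebo event is recorded after the Week 16 infusion, and so outside the controlled period, 4 and 1 meets it. The moved event cannot add to the Octagam count in this rule; it can only leave the placebo count.

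**The case against.** A reader might infer that a clot formed on placebo in Weeks 12 to 16 is looked for only after Octagam, is then automatically charged to Octagam, and so produces a false stop. The documents do not support that.

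- The adverse event tables go by treatment at the time of the event (Protocol 9.2.1, SAP 7), and SAP 11.1 defines treatment-emergence by onset or worsening. An event with onset before the Week 16 infusion stays with placebo, whenever it is found.
- Wells is not the only route to detection. Adverse events are asked about at every visit (7.3.2.2). Week 16 has a physical examination and vital signs before infusion, and Week 40/Drop-out has a physical examination. TEEs are reported as serious events. Many Wells items are signs that such an examination can find.
- The example counts and person-months are chosen, not documented. At one event per 173 placebo person-months, Weeks 12 to 16 (47 × 28/30.44 = 43.2 months) hold 43.2/173 = 0.25 expected events, or about a 22% chance of any (1 − e^−0.25). The event must then also be missed before infusion and dated by detection.
- Protocol version 12 is dated 18 June 2019, with clinical end planned for Q4 2019. Counting back 24 weeks from the end of December puts the last Week 16 visits at about mid-July 2019, so an amendment would reach few placebo intervals.

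Most of this stands, and it limits the point to a possibility. Three things remain. Section 6.2.3.1 works with TEEs *observed* and with the last treatment, and does not say that onset governs. Weeks 8 and 12, where switches occur, have no pre-infusion physical examination. And none of these arguments removes the contradiction over the closing visit.

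**Conclusion.** The point holds as an inconsistency with a bounded consequence. The detailed schedule omits a closing Wells score that Protocol 7.3.5.1 and SAP 11.5.2 call for. About 24 to 27 days after the last cycle therefore end without one, for completers and for subjects who leave at Week 16 without an infusion.

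Misattribution where treatment changes is possible only if the event escapes adverse event questioning and the pre-infusion assessments and is then dated by detection. The Ro/Rp wording leaves that open. The shift of 0.74 to 1.08 for one event is an upper bound in the sense that it takes the move as certain. It rests on 47 per arm with full placebo follow-up and on 200 to 600 assumed Octagam months. It shows that the rule is sensitive to a single event, not that a false stop is likely. The primary efficacy analysis and the sample size are unaffected.

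**What to change.** 1. Reconcile Table 1, Section 6.1.10 and Table 4 with Section 7.3.5.1 and SAP 11.5.2 by adding both Wells scores to the Week 40/Drop-out visit, including Week 16 when it is the termination visit. The PE score uses heart rate, and vital signs are not listed at Week 40/Drop-out either, so heart rate has to be recorded there.
2. Add a pre-infusion Wells score at the visits where treatment can change: the First Period switch visits (Weeks 8 and 12) and Week 16. Weeks 20 to 36 do not need one for this purpose, because everyone is already on Octagam.
3. State in Section 6.2.3.1 and SAP 11.1 that a TEE is attributed by onset date, and that one found through a pre-infusion score belongs to the treatment of the preceding interval.

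The cost is a few minutes per visit for a checklist already in use, an occasional extra Doppler scan under the existing rule, a short amendment and a sentence in the SAP. The attribution wording is useful even if few visits remain, since it can be settled before database lock.

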MedDRA	Medical Dictionary for Regulatory Activities
MMT	Manual Muscle Testing
NSAID	Non-Steroidal Anti- Inflammatory Drug
PE	Pulmonary Embolism
PM	Polymyositis
PP	Per Protocol
PVC	Polyvinyl Chloride
SAE	Serious Adverse Event
SAF	Safety Analysis Set
SAP	Statistical Analysis Plan
SF-36v2	Short Form 36 Items Health Status Version 2
SOP	Standard Operating Procedure
TEAE(s)	Treatment Emergent Adverse Event(s)
TEE(s)	Thromboembolic Event(s)
TIS	Total Improvement Score
TSH	Thyroid-stimulating hormone
VAS	Visual Analogue Scale
VTE	Venous Thromboembolism

1 INTRODUCTION

1.1 Immunoglobulins

Since more than 5 decades immunoglobulins have been used to provide antibodies for the prevention of viral and bacterial diseases (replacement therapy) in immunocompromised patients. Within the last 30 years intravenous immunoglobulins (IGIVs) have been proven to be useful in a wide variety of clinical conditions (other than classical replacement therapy), in which IGIVs exhibit an immunomodulatory effect. These include idiopathic thrombocytopenia in children and adults at high risk of bleeding or prior to surgery to correct the platelet count, Kawasaki disease and Guillain-Barré syndrome. More recently, single IGIV brands have also been licensed for chronic inflammatory demyelinating poly(radiculo)neuropathy and multifocal motor neuropathy. Experimental off-label use of IGIV in other neurological and dermatological indications is widespread.

Octagam 5% and Octagam 10% are liquid intravenous polyvalent IGIV preparations, which are prepared from human plasma and mainly contain human normal immunoglobulin G. The molecules are present in their native form, which is essential for their biological activity. Octagam 5% is approved since February 1995 and is currently marketed in 82 countries worldwide, while Octagam 10% got its first license in May 2008 and is now approved in 55 countries worldwide.

